Supervised Test-Product Application 				X	X	X	X	
Supervised Sunscreen Application 				X	X	X	X	
Products and Test Diary Return								X
Discharge from Study								X

 GlaxoSmithKline	Document Name	Protocol 206827 CCI doc		
	Type	Version	Document Identifier	Effective Date
	elido controlled	4.0; Most-Recent; Effective; CURRENT	090032d580d98eb9	15-Sep-2017 09:27:15
	Reason For Issue	Auto Issue		

1. For Visits 3-8, subjects will be instructed to cleanse their face at home using the cleanser provided and must not use any other product on their face, including the test product (Group I only) and sunscreen. Subjects will be instructed to bring the dispensed cleanser, sunscreen and test product (Group I only) with them to all visits. Subjects will be invited to the site in the morning (prior to 9 am) to avoid exposure to strong sunlight.
2. The Investigator or designee will review the diary to monitor and encourage compliance. Additional or missed product applications will be recorded as deviations. The Evaluator must be blind to diary review.
3. Exclusion Criteria 9 will not be included for this assessment. Exclusion criteria 9 is evaluated based on the results from the sensitivity test.
4. To include a review of the inclusion/exclusion criteria specified in Appendix 4. Subjects must be considered compliant with these inclusion/exclusion criteria in order to remain eligible for the study.
5. Peel regimen (70% Glycolic Acid facial peel solution, Bicarbonate Neutralizing Solution and Sunmax Sensitive SPF 50) to be applied to the volar forearm of each subject by a qualified dermatologist.
6. Assessments to be taken 45±15 minutes after completion of the study material sensitivity test.
7. Assessments to be taken 24±4 hours after completion of the study material sensitivity test.
8. Assessments to be taken 7 days after completion of the study material sensitivity test.
9. 70% Glycolic Acid facial peel to be administered by a qualified dermatologist who must be blind to randomization. The Glycolic Acid treatment and neutralizing solution will be sourced commercially by the study site.
10. Assessments to be taken 60±15 minutes after completion of the facial peel procedure.
11. Only subjects randomised to Group I will be dispensed test product. Subjects in Group I and II will be dispensed different test diaries to reflect the difference in treatment allocation. The washout diary will be returned at the same time as test diary dispensing.

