12. Test product application will occur immediately after the post-procedure, pre-treatment (Baseline) assessments are complete and under the supervision of the Investigator or designee to subjects in Group I, only. Subjects in Group II will not apply anything to their face. The Evaluator must be blind to test product application.
13. Measurements to be taken 180±15 minutes, 360±15 minutes, 24±4 hours, 48±4 hours, 72±4 hours, 168±4 hours and 336±4 hours after completion of the facial peel procedure. At Visit 3, there must be at least 30 minutes between test product application (Group I, only) and instrumental measurements.
14. Images to be captured 24±4 hours after completion of the facial peel procedure and at Visit 8 (Day 22).
15. Assessments to be taken 180±15 minutes, 24±4 hours, 48±4 hours, 72±4 hours, 168±4 hours and 336±4 hours after completion of the facial peel procedure.
16. Test product application will be conducted under the supervision of the Investigator or designee to subjects in Group I, only. Subjects in Group II will not apply the test product to their face.
17. Sunscreen application will be conducted under the supervision of the Investigator or designee to all subjects.

Document Name	Protocol 206827 CCI doc	Document Identifier	Effective Date
Type	Version		
eldo controlled	4.0; Most-Recent; Effective; CURRENT	090032d580d98eb9	15-Sep-2017 09:27:15

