Within the washout phase, a study material sensitivity test is included to identify subjects who may be sensitive to the study materials in order to determine whether they are suitable to undergo the facial peel procedure. A qualified dermatologist will dispense a thin layer of the 70% glycolic acid peel solution to cover a demarcated 5 x 5 cm square area on the volar surface of the forearm and, within a period of 30-60 seconds, will neutralize the 70% glycolic acid peel solution with the bicarbonate neutralizing agent and then rinse the skin thoroughly with water and pat dry with a soft towel. Once dry, the dermatologist will apply a thin layer of the Sunmax Sensitive SPF50 Sunscreen to the 5 x 5 cm square area. Dermatologist and subject self-assessments will be used to evaluate local tolerance. If subject data for the study material sensitivity study contains a dermatologist or subject self-assessment score of "Severe" for any attribute, this subject will be deemed to be in violation of exclusion criteria 9 and must be discharged from the study.

Upon completion of the washout phase, subjects considered to be eligible for the test phase will be randomised to two groups (Group I: Test product; Group 2: No-treatment) and a qualified dermatologist with experience administering facial peels will conduct the 70% Glycolic Acid procedure.

Subjects randomised to Group I will be instructed to apply the test product twice-daily (morning and evening) after cleansing, for a total of 14 consecutive days. All subjects will be instructed to continue using the facial cleanser twice-daily during the morning and evening, and to apply the sunscreen in the morning and at lunchtime. A summary of the subject's post-randomization regimen is included below for clarity.

Randomized Group	Morning	Lunchtime*	Evening
Group 1	1. Cleansing 2. Test Product 3. Sunscreen	1. Sunscreen	1. Cleansing 2. Test Product
Group 2	1. Cleansing 2. Sunscreen	1. Sunscreen	1. Cleansing

\*Lunchtime application must be at least 3 hours after previous sunscreen application

Subjects will not apply any sunscreen on the day of the facial peel procedure (Day 8), since they will remain at site until the evening (after 5 pm). On the morning of each visit, prior to arriving at the site, subjects will be instructed to cleanse their face and not to apply any test product or sunscreen until after all measurements and assessments have been completed. Before leaving the site, subjects will undergo

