### 5.4. Product Compliance

A daily dairy will be used to monitor and promote compliance. Subjects will not be excluded due to missed applications, but will be reminded to use the products as per the instructions provided and to complete the diary card on a daily basis to encourage compliance. Missed or additional product applications will be recorded by the

Document Name	Protocol 206827 CCI doc		
Type	Version	Document Identifier	Effective Date
eldo controlled	4.0; Most-Recent; Effective; CURRENT	090032d580d98eb9	15-Sep-2017 09:27:15
Reason For Issue	Auto Issue		

Investigator or designee as deviations. Subjects will be asked to bring their washout and test products to each site visit.

To be considered compliant and part of the per-protocol (PP) population, a subject must have used the test product and/or sunscreen at least 80% of the instructed number of applications following completion of the facial peel procedure.

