## 5.9. Packaging and Labelling

The Washout/ Reference products (Simple Kind to Skin Moisturising Facial Wash and Sunmax Sensitive SPF 50) and Test Product (Physiogel Calming Relief Restoring Lipid Balm) will be over-wrapped in opaque vinyl and any branding on the commercial products will be obscured.

A new label will be created by the Clinical Supplies Department, GSKCH and applied to each product. The contents of the label will be in accordance with all applicable regulatory requirements and will be the responsibility of the Clinical Supplies Department, GSKCH. Each study label will contain, but not be limited to, protocol number, product code letter for Test Product only and directions for storage.

Care should be taken with the supplied products and their labels so that they are maintained in good condition. It is important that all labels remain intact and legible for the duration of the study. Subjects should be instructed to not remove or deface any part of the study label.

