### **6.3.20. Supervised Test Product Application Post-Procedure**

Subjects randomized to test product (Group I) will be instructed to apply the test product as per the labelled usage instructions immediately after the post-procedure, pre-treatment (baseline) assessments are complete. The Investigator or designee will oversee this initial product application. Group II will not apply any test product. Product application will be recorded on the eCRF and subject diary and must happen at least 30 minutes prior to any further instrumental measurements. The Investigator or designee involved in this step must not be involved in any assessments in order to protect the blind.

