### 9.2. General Considerations

#### 9.2.1. Definition of Analysis Populations

All randomized subjects will be included in the intent-to-treat (ITT) population. All subjects with at least one application of product in the test phase (i.e. test product for subjects in Group I or sunscreen for subjects in Group II) will be included in the Safety population.

Document Name	Protocol 206827 CCI doc		
Type	Version	Document Identifier	Effective Date
elido controlled	4.0; Most-Recent; Effective; CURRENT	090032d580d98eb9	15-Sep-2017 09:27:15
Reason For Issue	Auto Issue		

Subjects will be considered eligible for a Per Protocol (PP) population if they were randomized, received at least one application of test product, had at least one post-procedure, post-treatment assessment available and were compliant with both test and washout products post-procedure. Other considerations for eligibility for the PP population including but not limited to use of concomitant medications will be detailed in the Statistical Analysis Plan prior to database unblinding.

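### The Per Protocol definition requires use of the test product in both arms, so no correctly treated no-treatment control can enter the Per Protocol set

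*Protocol*

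**What the plan says.** Section 9.2.1 of the protocol sets four joint conditions for the PP population. The subject must be "randomized, received at least one application of test product", must have at least one assessment after procedure and treatment, and must have complied with both test and washout products after the procedure. None of these conditions is limited to one group. Only further considerations, such as concomitant medication, are left to the SAP.

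The rest of the protocol is clear about who uses the test product:

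- Section 3.4 defines the arms as "Group I: Test product; Group 2: No-treatment".
- Schedule of Events, note 11: "Only subjects randomised to Group I will be dispensed test product".
- Section 6.3.20, for the first application at Visit 3: "Group II will not apply any test product".
- Schedule of Events, note 16, for the later supervised applications: "Subjects in Group II will not apply the test product to their face".

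Two other places bear on who was meant to be in the PP set. The Safety definition, also in section 9.2.1, counts exposure by group: "test product for subjects in Group I or sunscreen for subjects in Group II". Section 5.4 says that to be compliant and in the PP population, "a subject must have used the test product and/or sunscreen at least 80% of the instructed number of applications" after the peel.

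**The concern.** A PP set in a two-arm trial should hold the subjects in each arm who followed their assigned regimen. For Group II the assigned regimen is cleanser and sunscreen without the test product. A condition that demands test product use therefore removes every adherent control. The only controls it could let in are those who were given the test product in error, which is the reverse of what a PP set is for.

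The protocol has a between-group secondary objective (section 2) and between-group comparisons in section 9.3.3. A PP version of any of these, or a PP summary of Group II, would have no valid control arm if the definition were followed. An SAP that quietly admitted Group II would instead depart from a condition the protocol has fixed. Settling the point after unblinding would also expose the choice of controls to the charge of being data-driven.

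**Working it through.** This is a question of logic, with one count attached.

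**1. Can the term test product cover sunscreen?** No. The product tables in the synopsis and section 5.1 have three separate columns: cleanser, test product (the lipid balm) and sunscreen. Section 5.9 makes the same division, naming the washout and "Reference products (Simple Kind to Skin Moisturising Facial Wash and Sunmax Sensitive SPF 50) and Test Product" as distinct items. The Safety sentence in section 9.2.1 also treats test product and sunscreen as different things.

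**2. Apply the exposure condition to each arm.**

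| Arm, treated as assigned | Test product applications instructed | At least one application? |
|---|---|---|
| Group I | Twice daily for 14 days | Can be met |
| Group II | 0 | Cannot be met |

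**3. Does the compliance condition also exclude Group II?** Not necessarily. Where no test product applications are instructed, compliance with test product can be read as met by default. The exclusion therefore rests on the exposure condition alone, because zero applications can never be at least one.

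**4. Does section 5.4 rescue Group II?** No. Its and/or wording presupposes PP members who use sunscreen only, which shows the likely intent. But it sets an 80% compliance threshold and does not replace the separate exposure condition in section 9.2.1. The two sections disagree on whether Group II can be in the PP set.

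**5. Count on the planning figures.** Inputs from section 9.1: 40 completers per group, 5 per group given the incorrect treatment.

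- Correctly treated Group II completers: 40 − 5 = 35.
- Of these, meeting the exposure condition: 0 of 35.
- Mis-allocated Group II subjects who could meet it: at most about 5. The lower bound is 0, because they must also pass the assessment, compliance and SAP conditions.

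**6. The stated power, checked for completeness.** Section 9.1 states 80% power for a within-group TEWL change of 1.83, with SD 4.053 and two-sided alpha 0.05. For a one-sample t-test with n = 40:

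- Noncentrality = (1.83 / 4.053) × √40 ≈ 2.86.
- Power from the noncentral t distribution = 79.5% (normal approximation 81.5%).
- Change detectable at exactly 80% power = 1.84.

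The stated figure reproduces within rounding and does not depend on the PP definition.

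**The case against.** The strongest reply is that nothing specified in the protocol uses the PP set. Section 9.3 assigns it no analysis, the success rule in section 9.2.3 looks only at the test product group, and section 9.2.2 says that no data are excluded from any analysis. This stands, and it limits the seriousness of the point. It does not make the definition usable: the protocol chose to define a PP population and tied a compliance threshold to it.

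Second, the intent is recoverable. The Safety sentence, section 5.4 and the diary-review sections (for example 6.4.4, which restricts test product to Group I) all suggest a drafting slip, and the SAP could correct it. The intent is indeed plain, but the SAP has been left only further considerations. The exposure condition is already fixed in the protocol.

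Third, the mis-allocation scenario involves inference, since section 9.1 does not name the product that each affected subject received. In a two-arm trial, however, the wrong treatment for a Group II subject can only be the test product. How many such subjects would pass the other PP conditions is unknown, so the range of 0 to about 5 is as far as the documents go. The figure of 0 of 35 expresses the logical result as a count; it is not an effect size.

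Fourth, changing and/or in section 5.4 could narrow PP membership for Group I. That reading is already implied by section 9.2.1, which asks for compliance with both test and washout products. It is also true that the 80% threshold in section 5.4 does not mention the cleanser, although the cleanser is a washout product. Aligning the other wording leaves that gap open.

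**Conclusion.** The concern holds. As written, section 9.2.1 admits no correctly treated Group II subject to the PP population: 0 of about 35 on the planning figures. Between 0 and about 5 Group II subjects, all mis-allocated to the test product, could meet the exposure condition. The count assumes that the planned 40 completers and 5 mis-allocated subjects per group are realised, and that mis-allocated subjects are analysed in their randomised group. The zero itself needs no such assumption.

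The consequence is limited to PP summaries of Group II and PP between-group comparisons. The ITT and Safety populations, the success rule and the TEWL power statement are unaffected. This should be fixed, but it does not threaten the trial's primary conclusion.

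**What to change.** Make these wording changes before unblinding and carry them into the SAP:

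- **Section 9.2.1, exposure.** Require at least one application of product in the test phase, with the qualifier already used for the Safety population: "test product for subjects in Group I or sunscreen for subjects in Group II".
- **Section 9.2.1, compliance.** Require compliance with the test product for Group I only and with the washout products for all subjects. This keeps the existing cleanser and sunscreen condition.
- **Section 5.4.** Replace the and/or wording with test product and sunscreen for Group I, and sunscreen for Group II. State whether the 80% threshold also applies to the cleanser.
- **SAP.** Among the further PP considerations, say how the mis-allocated subjects are handled.

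No extra data or subjects are needed.

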#### **9.2.2. Exclusion of Data from Analysis**

No data will be excluded from any analyses.

#### **9.2.3. Criteria for Evaluation**

The primary evaluation of tolerance will be based on the Dermatologist global assessment. The trial will be considered a success if the majority (i.e. more than 50%) of subjects in the test product group have a favorable Dermatologist global assessment score.

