### Type and Planned Number of Subjects

Approximately 130 178 healthy females within the ages of 30 and 60 years (inclusive) with Fitzpatrick Skin Classification II-IV and moderate to advanced photo-damaged skin will be screened to randomize 80 100 subjects to ensure approximately 60 80 subjects (30-40 subjects per group) successfully complete the study. The sample size is based on clinical considerations and literature precedent [Narurkar, Schalka, Sulimovic, Kim]. With 30 subjects per treatment group, a change from baseline in Transepidermal Water Loss (TEWL) at least half the magnitude of the standard deviation (e.g. assume std=4 (ref. CCI [REDACTED])), and 2.1 point mean change from baseline) can be detected at two-sided alpha=0.05 with 80% power.

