## 9. STATISTICAL CONSIDERATIONS AND DATA ANALYSES

### 9.1 Sample Size Determination

Approximately 130 **178** healthy females within the ages of 30 and 60 years with Fitzpatrick Skin Classification II-IV and moderate to advanced photo-damaged skin will be screened to randomize 80 **100** subjects to ensure approximately 60 **80** subjects (**30 40** subjects per group) successfully complete the study. The sample size is based on clinical considerations and literature precedent [Narurkar, Schalka, Sulimovic, Kim].

~~With 30 subjects per treatment group, a change from baseline in TEWL at least half the magnitude of the standard deviation (e.g. assume std=4 (ref. **CCI** [REDACTED]), and 2.1 point mean change from baseline) can be detected at two-sided alpha=0.05 with 80% power.~~

**THE FIRST 10 SUBJECTS WERE MIS-ALLOCATED TREATMENT. TO PROTECT THE STATISTICAL POWER OF THE STUDY FOR THE SECONDARY TEWL ENDPOINT, 20 ADDITIONAL SUBJECTS WILL BE RECRUITED INTO THE STUDY. WITH 100 SUBJECTS RANDOMISED, 80 SUBJECTS (40 SUBJECTS PER GROUP) ARE EXPECTED TO COMPLETE THE STUDY.**

**WITH 40 SUBJECTS PER TREATMENT GROUP WITH 5 SUBJECTS PER GROUP RECEIVING THE INCORRECT TREATMENT DUE TO MIS-ALLOCATION, A WITHIN CHANGE FROM BASELINE IN TEWL OF 1.83 CAN BE DETECTED AT TWO-SIDED ALPHA=0.05 WITH AN SD=4.053 AND 80% POWER.**

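### Amendment 1 does not say how the ten mis-allocated women are grouped for the primary tolerance criterion; by default, non-users of the product enter its success rate

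*Protocol*

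**What the plan says.** Section 9.1, as amended, states: "THE FIRST 10 SUBJECTS WERE MIS-ALLOCATED TREATMENT". It expects that "WITH 100 SUBJECTS RANDOMISED, 80 SUBJECTS (40 SUBJECTS PER GROUP) ARE EXPECTED TO COMPLETE THE STUDY" and gives the power statement for a TEWL change "WITH 40 SUBJECTS PER TREATMENT GROUP WITH 5 SUBJECTS PER GROUP RECEIVING THE INCORRECT TREATMENT DUE TO MIS-ALLOCATION". The wrongly treated women are thus counted within the 40 per group. The section gives the purpose of the extra recruitment as protecting power for TEWL, a secondary endpoint.

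Section 9.2.1 says "All randomized subjects will be included in the intent-to-treat (ITT) population", and section 9.2.2 says "No data will be excluded from any analyses".

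The primary criterion in section 9.2.3 calls the trial a "success if the majority (i.e. more than 50%) of subjects in the test product group" have a favourable dermatologist global score. Section 9.3.2 summarises that proportion, with a 95% confidence interval, for each product group, and allows an optional chi-square comparison. Neither section names an analysis population or says whether group means the arm assigned or the regimen used.

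The Protocol Amendment Page lists the sections changed by Amendment 1 as the synopsis, 3.3 and 9.1. Sections 9.2.3 and 9.3.2 are not among them.

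**The concern.** The primary objective is the local tolerance of the test product. Under section 6.8.10 the dermatologist rates the regimen a woman followed, including new signs or symptoms arising while she used it. A rating from a woman who did not apply the balm says nothing about how the balm is tolerated.

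If the ten are counted by assigned arm, about five such ratings enter the product's tolerance rate, and five ratings of the product are credited to no-treatment. For efficacy, this kind of dilution is usually conservative. For tolerance it works the other way: if the product irritates, its rate is pulled up towards the no-treatment rate, and intolerance among the five actual users in Group II is charged to the control arm. The sole success criterion would then no longer be a bar on women who used the product.

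**Working it through.** **Inputs.** From 9.1: 40 completers per group, 5 of them wrongly treated; TEWL change 1.83, SD 4.053, two-sided alpha 0.05, power 80%. From 9.2.3: success if more than 50% are favourable. From the superseded sample-size statement, still visible in the synopsis: SD 4 and "2.1 point mean change from baseline) can be detected at two-sided alpha=0.05 with 80% power". Assumed, because the protocol gives no figures: the true tolerance rates of users and non-users.

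**Step 1: reproduce the plan's figure.** Section 9.1 says a within-group "CHANGE FROM BASELINE IN TEWL OF 1.83 CAN BE DETECTED AT TWO-SIDED ALPHA=0.05 WITH AN SD=4.053 AND 80% POWER". For a one-sample t-test the noncentrality is 1.83/4.053 × √n.
- n = 40: noncentrality 2.856, power 79.5%, in line with the stated 80%.
- n = 35, leaving the five out: noncentrality 2.671, power 73.7%.

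The stated power therefore needs the five kept in each group. The effect and SD also look diluted for this purpose. Taking the superseded change of 2.1 and SD of 4, with 5 of 40 showing no change:
- mean: 2.1 × 35/40 = 1.84 (stated 1.83)
- SD: √(16 + 2.1² × 35 × 5/40²) = 4.06 (stated 4.053)

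Section 9.1 thus appears to have been calculated with the mis-allocated women in their assigned arms.

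**Step 2: carry that grouping to the success rule.** More than 50% of 40 means at least 21 favourable. In the assigned test product group there are 35 users and 5 non-users.
- All five non-users favourable: 21 − 5 = 16 users needed; 16/35 = 45.7%.
- No non-user favourable: 21 users needed; 21/35 = 60.0%.
- Grouped by regimen applied (35 + 5 = 40 users): 21/40 = 52.5%.

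**Step 3: chance of meeting the rule.** As assigned, this is P(X + Y ≥ 21) with X ~ Bin(35, user rate) and Y ~ Bin(5, non-user rate). By regimen applied, it is P(Bin(40, user rate) ≥ 21).

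| True user tolerance (assumed) | As assigned, non-users 90% to 100% tolerant (assumed) | By regimen applied |
|---|---|---|
| 45% | 46.6% to 53.1% | 21.3% |
| 50% | 69.0% to 75.0% | 43.7% |
| 60% | 95.2% to 97.0% | 87.0% |
| 70% | 99.8% to 99.9% | 99.4% |
| 80% | about 100% | about 100% |

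**Step 4: difference between arms.** With 5 of 40 swapped in each arm, the expected observed difference is (35 − 5)/40 = 0.75 of the true one. For illustration, with 70% tolerance on product and 95% without:
- test product arm: (35 × 0.70 + 5 × 0.95)/40 = 73.1%
- no-treatment arm: (35 × 0.95 + 5 × 0.70)/40 = 91.9%

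A true gap of 25 points appears as 18.75 points. This attenuation does not depend on the assumed rates.

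**The case against.** A reader might infer that the protocol fixes the rule, so that five women who never used the product do count towards its success. The text does not go that far. No population is named for the primary criterion, and ITT membership does not say under which label a wrongly treated woman is counted. The group of 40 with five wrongly treated is an input to a TEWL calculation, not a statement about counting tolerance. The words test product group could be read as product used. That the five used no product is itself inferred: 9.1 speaks only of incorrect treatment, and in this design the only other regimen is no test product. All of this stands.

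The SAP, which is not shown, may settle the grouping, since 9.3 defers detail to it. That is possible. However, the protocol itself fixes the success criterion, and the amendment that records the error leaves the criterion open to two readings.

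The per-protocol definition in 9.2.1 requires at least one application of test product, so it would drop Group I women who used none. This helps only partly: that population is not named for the primary analysis, and it does not return the Group II users to the product arm.

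The effect on pass/fail is confined to rates near 50%, and nothing in the protocol suggests a rate that low; section 3.4 cites favourable tolerance and post-marketing data. This stands too. The 45.7% figure is one extreme of a range whose other end is 60.0%.

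It would also be wrong to read 9.2.2 as blocking a regrouping, because regrouping excludes no data. Nor is as-treated grouping required for the between-group comparison: that comparison is optional, and analysis as randomised is a standard choice for it.

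**Conclusion.** The concern holds as a gap left by Amendment 1 whose default reading suits the tolerance endpoint badly. Taken together, 9.1, the ITT definition and the no-exclusion rule point most naturally to grouping by assigned arm. On that reading 12.5% of the ratings in the test product group say nothing about the product, the bar on actual users lies anywhere from 45.7% to 60.0%, and any true difference between arms is shown at three quarters of its size.

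The consequence for the success decision is limited. It is large at an assumed user tolerance of 45% (47% to 53% against 21%), moderate at 60% (95% to 97% against 87%) and almost nil at 70% or more. The reported rate and its interval are affected whenever the arms differ.

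These figures assume a full swap of five and five, that all ten women complete (as 9.1 does), and that the incorrect treatment for a Group I woman meant no test product. This should be fixed as a cheap improvement; it is not a fault that undermines the trial.

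**What to change.** In 9.2.3 and 9.3.2, name the analysis population and state that the tolerance proportion, its confidence interval and the success rule are computed by the regimen actually applied. Under a full five-and-five swap each arm still has 40 women. Report the as-assigned result alongside. The optional between-group comparison may stay as randomised, with the as-treated version shown next to it.

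A further sensitivity analysis without the first ten women is useful; only for that does 9.2.2 need a change.

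The cost is a few sentences in the protocol and SAP and two extra tables, with no new data. The downside is that the main tolerance table departs from the assigned groups for ten women, which the as-assigned result makes visible.
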